7.3. Migraine and pregnancy outcomes

Migraine itself has been associated with an increased risk of some adverse pregnancy outcomes. A population-based cohort study using Danish population registries identified 22,841 pregnancies among women with migraine and an age- and conception year-matched comparison cohort of 228,324 pregnancies among women without migraine.¹⁵ Compared to the women without migraine, women with migraine, regardless of treatment type, were shown to have an increased risk of pregnancy-associated hypertension disorders and miscarriage, and an increased prevalence of low birth weight, preterm birth, and cesarean delivery, but not for small for gestational age (SGA) and MCMs. The prevalence of any MCM was 3.1% in women with and without migraine. Offspring who were prenatally exposed to maternal migraine had elevated risks of intensive care unit admission, hospitalization, dispensed prescriptions, respiratory distress syndrome, and febrile seizures, but not of death and cerebral palsy. The results suggested that migraine itself, rather than its treatment, is associated with adverse pregnancy and Infant outcomes.¹⁵

Other investigators have similarly reported associations between migraine and gestational hypertension, pre-eclampsia,¹⁶ low birth weight,^{8,16-18} and preterm birth.^{8,16} In earlier studies, women with migraine were reported to be at an increased risk of developing hypertensive disorders such as pre-eclampsia in pregnancy compared to women without migraine,^{19,20} which is associated with an increased risk of low birth weight, preterm birth, and SGA infants.²⁰⁻²² In the migraine population, more severe migraine,

PFIZER CONFIDENTIAL

defined by greater frequency and intensity, was shown to be associated with an increased prevalence of cardiovascular comorbidities and comorbid affective disorders such as anxiety and depression.^{23,24} In the US general population, the estimated background risk of MCMs and miscarriage in clinically recognized pregnancies is 2%–4% and 15%–20%, respectively. The estimated rates of MCMs (2.2% to 2.9%) and miscarriage (17%) among deliveries to women with migraine are similar to rates reported in women without migraine.¹⁴

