9.3.4. Outcomes

9.3.4.1. Congenital malformations

The study will define and code congenital malformations using the criteria specified by the CDC MACDP and EUROCAT.^{40,41} A malformation may be described and classified by severity (eg, major malformation), by origin (eg, genetic, environmental exposure), and by organ system (eg, urogenital system or malformations known as congenital heart defects [CHD]). An MCM will be defined as any major structural or chromosomal defect detected in live-born infants, stillbirths/fetal losses ≥ 20 gestational weeks, and elective terminations of any gestational age.⁴⁰ This definition is consistent with, but not restricted to, the CDC MACDP and EUROCAT definitions.

To avoid misattribution of the malformation to the medication, MCMs not associated with medication exposure, such as chromosomal abnormalities, genetic syndromes, prematurity-related conditions in infants born at < 36 gestational weeks (eg, patent ductus arteriosus, patent foramen ovale, inguinal hernias, or undescended testes), and positional effects (eg, hip dislocation due to breech position or abnormal skull shape due to crowding by multiple fetuses), will not be considered MCMs in the statistical analyses comparing MCM prevalence between the internal cohorts.⁴² Given that the registry will also use the CDC's MACDP and EUROCAT as external comparators, the registry will include cases of MCMs not associated with medication exposure in the prevalence calculations for this comparison.

Transient malformations in term infants, whether occurring alone or with other malformations, will be reported in the study, as certain transient malformations may be associated with maternal medication exposure in pregnancy and can vary by age of detection and/or age of resolution (eg, CHDs).⁴³ Lastly, the MACDP only includes minor malformations if they occur in the presence of an MCM. However, as stated in the objectives, major and minor malformations are of interest for this study and both will be reported.

Live-born infants with only positional defects (malformations), infectious conditions, or with biochemical abnormalities will be classified and reported separately. The CDC MACDP has different objectives and reporting needs than this project, so a thoughtful adaptation of their guidelines is appropriate.

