9.5.2. Full study

The full study will aim to prospectively enroll a minimum of 390 women with migraine who were exposed to rimegepant during pregnancy or just prior to pregnancy (up to 3 days prior to conception), as well as an internal comparison cohort consisting of 390 women with migraine who were not exposed to rimegepant during pregnancy or just prior to pregnancy (up to 5 product half-lives prior to conception). The target sample size for the registry is based on the primary outcome, MCM, which is also the outcome with the most restrictive denominators and 1 of the lowest prevalence rates in the general population. If all are evaluable for potential MCMs (evaluable being those for whom pregnancy outcome and major/minor congenital malformation assessments are obtained), and assuming an approximate 3% overall population prevalence of MCM, ⁵⁴ at α =0.05, this sample size provides 80% power to detect a 2.5-fold increased risk for overall MCM. Most registry power calculations are performed for overall MCM to detect an increased risk between 2- and less than 3-fold.⁵⁵ A midpoint threshold of a 2.5-fold increased risk was selected for this study. Assumptions for study calculations are consistent with those applied in the retrospective pregnancy outcomes study (NDA 212728, postmarketing requirement 3799-7, Pfizer study C4951006 [formerly BHV3000-403]).

Prospective enrollment can occur only after pregnancy is recognized but while the pregnancy is ongoing. Therefore, early pregnancy losses will not be captured, and a live birth rate higher than that of the general population would be expected. Research shows that approximately 90% of pregnancies enrolled in pregnancy exposure registries result in a live birth.^{56,57} Assuming that 90% of prospectively enrolled pregnancies result in live births and 10% are lost to follow-up,⁵⁸ at α =0.05, the study sample of 390 prospectively enrolled pregnant women in each internal cohort would result in 316 evaluable participants per cohort. Therefore, the study would have 80% power to detect a 2.7-fold increased risk of overall MCM (Table 2).

PFIZER CONFIDENTIAL

Outcome	N per cohort	Reference rate	Relative risk detectable	Power ^b
МСМ	390	3% ^{54,55,59}	2.5	80.6%
МСМ	316 ^a	3% ^{54,55,59}	2.7	80%

Table 2.	Sample Size and Power Estimates for Primary	Outcome, MCM

MCM = major congenital malformation; reference rate = prevalence rate of outcome in general population for pregnant women of any age

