9.7.3.3. Calculation of outcome prevalence

Prevalence rates of the outcomes of interest will be calculated according to the conventions described in Table 4. In general, the prevalence of each outcome will be calculated by dividing the number of cases of the outcome by the appropriate denominator for that particular outcome, based on clinical knowledge and/or the methodology used by the external comparator. Prevalence is preferred over incidence when examining pregnancy outcomes, such as congenital malformations, because incidence cannot be reliably estimated given the complexities in the reproductive process.⁶⁷

For most outcomes, the main analysis population (denominator) will be the number of pregnant women with pregnancy outcome data, the number of live births, or the number of infants with follow-up data at the timepoint of interest, as appropriate; however, for some outcomes, the main analysis population (denominator) will be restricted based on certain relevant factors:

- For MCM, prevalence in the rimegepant-exposed cohort will be calculated among the subset of women who are exposed during the first trimester.
- For MCM, prevalence will be calculated among live births for the primary analysis, and a secondary analysis will be conducted among live births and fetal losses.
- For preterm birth, SGA, and postnatal growth deficiency, prevalence will be calculated among singleton live births due to the higher risk of these outcomes in twins and higher-order multiples.
- For live birth and infant outcomes (ie, preterm birth, SGA, postnatal growth deficiency, and infant developmental delay), prevalence will be calculated among live births/infants without MCMs.
- For postnatal growth deficiency, infants born preterm or SGA will be excluded from the main analysis population (denominator).
- For infant developmental delay, infants born preterm will be excluded from the main analysis population (denominator).
- For SAB and preterm birth, prevalence will be calculated among the subset of women who are enrolled in the registry prior to 20 and 37 gestational weeks, respectively.
- For some outcomes, prevalence will be calculated at multiple timepoints. For example, postnatal growth deficiency and infant developmental delay will be assessed at 2, 4, 6, and 12 months of

PFIZER CONFIDENTIAL

infant age. At each timepoint, prevalence will be calculated among infants with data available for the particular outcome at that timepoint.

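### The 80% power for a 2.7-fold MCM risk is computed for any-time exposure and overall MCM at 3%, not for the first-trimester, restricted-MCM comparison named as the primary analysis

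*Protocol*

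**What the plan says.** Protocol section 9.5.2 sets the target: "The full study will aim to prospectively enroll a minimum of 390 women with migraine who were exposed to rimegepant", with 390 unexposed women as the internal comparator. A woman qualifies as exposed with a dose at any time in pregnancy or up to 3 days before conception (section 9.2.1).

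The power calculation starts from "assuming an approximate 3% overall population prevalence of MCM". Its second step is "Assuming that 90% of prospectively enrolled pregnancies result in live births and 10% are lost to follow-up", so that "390 prospectively enrolled pregnant women in each internal cohort would result in 316 evaluable participants per cohort". The conclusion is "Therefore, the study would have 80% power to detect a 2.7-fold increased risk of overall MCM". Table 2 shows this row, and also a row with 390 per cohort, a 2.5-fold risk and 80.6% power. Table 3 repeats the 80.6%. The footnotes give a two-sided 0.05 level and a normal approximation.

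The primary analysis is defined elsewhere:

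- **Exposed denominator (section 9.7.3.3):** "For MCM, prevalence in the rimegepant-exposed cohort will be calculated among the subset of women who are exposed during the first trimester". Table 4 makes the primary analysis one of live births with first-trimester exposure. Any-time exposure is a secondary analysis.
- **Numerator (section 9.3.4.1):** chromosomal abnormalities, genetic syndromes, prematurity-related conditions and positional effects "will not be considered MCMs in the statistical analyses comparing MCM prevalence between the internal cohorts". They are kept for the comparisons with the birth-defect surveillance programmes.
- **Population (sections 9.3.1.1 and 9.7.1):** invalid participants, and women exposed to an excluded product after enrolment, are left out.

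**The concern.** The calculation describes one comparison and the protocol tests another. Section 9.5.2 calls MCM the outcome with the most restrictive denominators, but the restriction specific to the exposed cohort, first-trimester exposure, does not enter the 316. The 3% is an overall MCM rate in the general population, and Table 4 tests a narrower endpoint. Section 7.3 gives "The estimated rates of MCMs (2.2% to 2.9%) and miscarriage (17%) among deliveries to women with migraine", a range lying below 3%.

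The registry's target size rests on this outcome. If the planned analysis has less power than stated, the 390 target looks better justified than it is, and a finding of no difference may be given more weight against a 2.7-fold risk than it deserves.

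**Working it through.** **Inputs from the protocol.** 390 enrolled per cohort; live-birth factor 0.9; follow-up factor 0.9; reference rate p0 = 3%; relative risks 2.5 and 2.7; two-sided 0.05; normal approximation (section 9.5.2, Tables 2 and 3).

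**Formula.** With n0 comparator births, n1 exposed births, p1 = RR × p0 and pooled rate p̄:

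- SE0 = √[p̄(1 − p̄)(1/n0 + 1/n1)]
- SE1 = √[p0(1 − p0)/n0 + p1(1 − p1)/n1]
- power = Φ[(p1 − p0 − 1.96 × SE0)/SE1]

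**Step 1: reproduce the protocol.**

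- 390 × 0.9 × 0.9 = 315.9, that is 316.
- 390 per cohort, 3% against 7.5%: SE0 = 0.01597, SE1 = 0.01589, z = (0.045 − 0.03130)/0.01589 = 0.862, power 80.6%. Stated: 80.6%.
- 316 per cohort, 3% against 8.1%: SE0 = 0.01821, SE1 = 0.01810, z = (0.051 − 0.03570)/0.01810 = 0.845, power 80.1%. Stated: 80%.

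Both rows of Table 2 are correct for their inputs. The 390 row holds only if every enrolled woman is evaluable. At 316 per cohort, power for the 2.5-fold risk is 71.9%.

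**Step 2: first-trimester restriction.** Let s be the share of exposed live births with first-trimester exposure, so n1 = 316 × s. The comparator stays at 316. The protocol gives no value for s. Example with s = 0.8 (253 exposed births) at 3%: SE0 = 0.01885, SE1 = 0.01965, z = (0.051 − 0.03694)/0.01965 = 0.716, power 76.3%.

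**Step 3: reference rate.** The protocol gives no rate for the restricted endpoint. Example at 2.2% with s = 1: p1 = 5.94%, SE0 = 0.01572, SE1 = 0.01565, z = (0.0374 − 0.03081)/0.01565 = 0.421, power 66.3%.

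**Step 4: both together.** Power at RR 2.7, with the relative risk detectable at 80% power in brackets. Shares and rates are assumptions. 2.2% and 2.9% are the ends of the migraine range in section 7.3, and 3.1% is the Danish cohort figure in the same section.

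| Rate | s = 100% (316) | 90% (284) | 80% (253) | 60% (190) |
|---|---|---|---|---|
| 3.1% | 81.5% (2.7) | 79.7% (2.7) | 77.7% (2.8) | 72.3% (2.9) |
| 3.0% | 80.1% (2.7) | 78.3% (2.7) | 76.3% (2.8) | 70.9% (3.0) |
| 2.9% | 78.7% (2.7) | 76.9% (2.8) | 74.8% (2.8) | 69.5% (3.0) |
| 2.5% | 72.1% (2.9) | 70.4% (3.0) | 68.4% (3.0) | 63.2% (3.2) |
| 2.2% | 66.3% (3.1) | 64.6% (3.2) | 62.8% (3.2) | 58.0% (3.4) |

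**Step 5: test.** Section 9.7.3.1 plans exact methods for the crude relative risk. Fisher's exact test by full enumeration, 316 per cohort, 3% against 8.1%, gives 76.6%.

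**The case against.** Several points on the other side carry weight.

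- **No calculation error.** A reader might infer that Table 2 is miscalculated. It is not; both rows reproduce.
- **Not the only power statement.** Table 2 has two MCM rows and Table 3 repeats one of them.
- **The rate.** Section 7.3 also reports 3.1% for any MCM in women with and without migraine in a Danish registry cohort, and a US background of 2% to 4%. So 3% is defensible for overall MCM, and at 3.1% with all 316 exposed power is 81.5%. It is also tempting to read 2.2% to 2.9% as the rate for the restricted endpoint, but the protocol does not say that range applies the exclusions of section 9.3.4.1. The direction of the numerator effect is clear; its size is not in the document.
- **The share.** The 80% and 60% shares are assumptions. Section 9.2 asks for enrolment as early as possible, and section 7 notes that migraine may become less frequent after the first trimester. Both make a high share plausible. At 90% and a 3% rate the loss is about 2 points.
- **Other losses and gains.** Section 9.2.2 expects little use of several such products in one pregnancy. Each infant of a multiple pregnancy is counted, and 390 is a minimum. None of this is quantified, and it may partly cancel.
- **A narrower endpoint can sharpen the effect.** Removing defects that a drug does not cause may raise the true relative risk. The protocol's claim, though, is made at a fixed 2.7.
- **The test.** Section 9.7.3.1 does not name Fisher's test as the primary test, and it also plans a weighted log-binomial model. The exact figure bears on the crude comparison only.
- **Interpretation.** Relative risks are reported with 95% confidence intervals, so what a null result excludes is read from the interval. Section 9.9 already warns about small numbers and about dilution in a composite endpoint.

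What stands is that section 9.5.2 offers its figure without saying that the primary analysis is narrower in both denominator and numerator.

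**Conclusion.** The point holds as a mismatch between planning assumptions and the primary analysis. Table 2 is arithmetically sound, but the stated 80% power for a 2.7-fold risk is not supported for the primary analysis as defined. At 80.1% there is no margin. A first-trimester share below 100%, or a rate for the restricted endpoint below 3%, takes power under 80% unless the other input offsets it.

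The size is uncertain. Over rates of 2.2% to 3.1% and shares of 60% to 100%, power runs from 58.0% to 81.5% and the detectable relative risk from about 2.7 to 3.4. The low end combines the lowest rate with the lowest share, and a reader should not take it as the registry's expected power. The mismatch itself is certain because both sides are fixed in the protocol; the magnitude rests on the assumed share and rate.

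**What to change.** Restate section 9.5.2 and Table 2 for the primary analysis set:

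1. State that the denominator in the exposed cohort is first-trimester-exposed live births. Give an assumed share with its justification, or show shares of 100%, 90%, 80% and 60%.
2. Use a reference rate meant for the restricted MCM definition, or show 2.2% to 3.1%, and say that the migraine range and the 3% are not known to apply the same exclusions.
3. For each combination, give power at a relative risk of 2.7 and the relative risk detectable at 80% power.
4. Label the 390, 2.5-fold, 80.6% row in Table 2, and its repeat in Table 3, as assuming every enrolled woman is evaluable.
5. Mention the unquantified exclusions (invalid participants, later use of excluded products), and add the exact-test power (76.6% at 316 per cohort and 3%) as a supplementary line for the crude comparison.

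The cost is a text and table amendment and a less favourable stated power. No added enrolment is needed if that figure is accepted. If 80% power at 2.7-fold is to be kept, the same formula with the 0.81 retention factor asks for about 430 per cohort (3%, 80% share), 473 (2.5%, all first-trimester) or 521 (2.5%, 80% share).

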^a Assumes that 90% of prospectively enrolled pregnancies result in live births and 10% are lost to follow-up, resulting in 316 evaluable participants

^b Power calculations based on normal approximation, 2-tailed, α =0.05⁶⁰

Additionally, Table 3 shows that, without any adjustments for multiple comparisons, the proposed sample size (390 pregnant women) will afford the study >80% power to detect a 2.5-fold increase in all other outcomes except eclampsia, stillbirth, and TOPFA (for which the study will have <20% power to detect a 2.5-fold increase).

Table 3.	Power Calculations
----------	---------------------------

Outcome	Reference rate	Power estimate ^a
MCM ^{54,55,59}	3%	80.6%
Gestational diabetes ²⁹	6.9%	>99.0%
Gestational hypertension ⁶¹	6.5%	>99.0%
Pre-eclampsia ⁶²	3.40%	85.5%
Eclampsia ⁶¹	0.3%	2.7% ^b
SAB ⁶³	13.4%	>99.0%
Stillbirth ⁶⁴	0.596%	12.6% ^b
Elective termination ⁶⁵	18.6%	>99.0%
TOPFA ⁶⁶	0.4%	5.8% ^b
Preterm birth ²⁹	8.47%	>99.0%
SGA*	10.0%	>99.0%
Postnatal growth deficiency*	10.0%	>99.0%

MCM = major congenital malformation; reference rate = prevalence rate of outcome in general population for pregnant women of any age; SAB = spontaneous abortion; SGA = small for gestational age; TOPFA = termination of pregnancy for fetal anomaly.

*By Definition

^a Power calculations were conducted using nQuery and were based on normal approximation, 2-tailed, alpha 0.05.

^b Fisher's Exact test was used for power calculation.

PFIZER CONFIDENTIAL

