Primary analysis between internal cohorts	Pre-eclampsia among women with pregnancy outcome data	Women with pregnancy outcome data
Eclampsia	·	
Primary analysis between internal cohorts	Eclampsia among women with pregnancy outcome data	Women with pregnancy outcome data
Comparison with external comparator ⁶¹	Eclampsia among live births	Live births among women with pregnancy outcome data
Pre-eclampsia/eclampsia	•	
Primary analysis between internal	Pre-eclampsia or eclampsia among	Women with pregnancy outcome

PFIZER CONFIDENTIAL

Outcome	Numerator	Denominator
cohorts	women with pregnancy outcome data	data
Comparison with external comparator (Pfizer Study C4951006)	Pre-eclampsia or eclampsia among women with pregnancy outcome data	Women with pregnancy outcome data
SAB		
Primary analysis between internal cohorts	SABs among women with pregnancy outcome data who are enrolled (and exposed, if applicable) prior to 20 gestational weeks	Women with pregnancy outcome data who are enrolled (and exposed, if applicable) prior to 20 gestational weeks
Comparison with external comparator (Pfizer Study C4951006)	SABs among women with pregnancy outcome data who are enrolled (and exposed, if applicable) prior to 20 gestational weeks	Women with pregnancy outcome data who are enrolled (and exposed, if applicable) prior to 20 gestational weeks
Stillbirth		
Primary analysis between internal cohorts	Stillbirths among women with pregnancy outcome data	Women with pregnancy outcome data
Comparison with external comparator (CDC NVSS)	Stillbirths among women with pregnancy outcome data	Live births and stillbirths among women with pregnancy outcome data
Comparison with external comparator (Pfizer Study C4951006)	Stillbirths among women with pregnancy outcome data	Women with pregnancy outcome data
Elective termination		
Primary analysis between internal cohorts	Elective terminations among women with pregnancy outcome data	Women with pregnancy outcome data
Comparison with external comparator (CDC Abortion Surveillance System)	Elective terminations among women with pregnancy outcome data	Live births among women with pregnancy outcome data
Comparison with external comparator (Pfizer Study C4951006)	Elective terminations among women with pregnancy outcome data	Women with pregnancy outcome data
TOPFA		
Primary analysis between internal cohorts	TOPFA among women with pregnancy outcome data	Women with pregnancy outcome data

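### Table 3's power for secondary outcomes ignores the 10% loss assumed in the same section and uses SAB and termination rates that do not fit its 90% live-birth assumption, so several stated powers are too high

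*Protocol*

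**What the plan says.** Section 9.5.2 sets a 1:1 design: 390 exposed women "as well as an internal comparison cohort consisting of 390 women with migraine who were not exposed to rimegepant". The effect size comes from the statement that "A midpoint threshold of a 2.5-fold increased risk was selected for this study".

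For the primary outcome, major congenital malformation (MCM), the section works through attrition. It says that "Research shows that approximately 90% of pregnancies enrolled in pregnancy exposure registries result in a live birth", expects more live births than in the general population because early losses are missed, and assumes 10% loss to follow-up. This gives 316 evaluable per cohort, and Table 2 accordingly raises the detectable risk from 2.5-fold to 2.7-fold.

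For the secondary outcomes the section makes no such step. It states that 390 women "will afford the study >80% power to detect a 2.5-fold increase in all other outcomes except eclampsia, stillbirth, and TOPFA". The footnotes to Table 3 say that "Power calculations were conducted using nQuery and were based on normal approximation, 2-tailed, alpha 0.05", and for the rare outcomes that "Fisher's Exact test was used for power calculation". Reference rates are defined as general-population prevalences. They include SAB 13.4%, elective termination 18.6%, stillbirth 0.596% and pre-eclampsia 3.40%. Power is given as over 99.0% for SAB, termination, gestational diabetes and gestational hypertension, and 85.5% for pre-eclampsia.

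Section 9.7.1 removes women lost to follow-up from the main analysis population. Table 4 in Section 9.7.3.3 gives each outcome its own denominator. For SAB it is women enrolled before 20 weeks. For termination and pre-eclampsia it is all women whose pregnancy outcome is known.

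**The concern.** Two sets of assumptions stand side by side in one section. The MCM calculation uses registry assumptions: 90% live births and 10% loss. The table for the secondary outcomes uses neither. Its SAB and termination rates, taken together, describe a population in which roughly a third of pregnancies do not end in a live birth.

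What is at stake is how a non-significant secondary result is read. The table tells a reader that a 2.5-fold increase in SAB or termination would almost certainly be detected, and the section's own live-birth assumption does not support that for both. The >80% sentence is also worded more widely than the table. Minor malformations and infant developmental delay are listed secondary outcomes (Section 8.3.2), but Table 3 gives neither a rate nor a power for them.

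**Working it through.** **Inputs.** From Section 9.5.2: n = 390 per cohort, relative risk 2.5, two-sided α = 0.05, normal approximation, 90% live births, 10% loss, and the Table 3 reference rates. Denominators are from Table 4.

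**Formula.** With p₁ the reference rate, p₂ = 2.5p₁ and p̄ their mean (pooled variance, no continuity correction):

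power = Φ{ [ (p₂ − p₁)√n − 1.96√(2p̄(1 − p̄)) ] / √( p₁(1 − p₁) + p₂(1 − p₂) ) }

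**Step 1: reproduce Table 3.** For pre-eclampsia, p₁ = 0.034, p₂ = 0.085 and p̄ = 0.0595. At n = 390: (0.051 × √390 − 0.656) / 0.3326 = (1.007 − 0.656) / 0.3326 = 1.057, and Φ = 85.5%, as stated. MCM gives 80.6%, gestational hypertension 99.1% and gestational diabetes 99.4%. Fisher's test gives 2.7% for eclampsia, 12.6% for stillbirth and 5.8% for termination for fetal anomaly. All agree with the table, so it uses 390 with no loss.

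**Step 2: apply the section's own loss.** Women with a known outcome: 390 × 0.9 = 351. Live births among them: 351 × 0.9 = 315.9, or 316. For pre-eclampsia at 351: (0.9555 − 0.6557) / 0.3326 = 0.901, and Φ = 81.6%.

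| Outcome | Stated at 390 | n after loss | Recomputed |
|---|---|---|---|
| Pre-eclampsia | 85.5% | 351 | 81.6% |
| Gestational hypertension | >99.0% | 351 | 98.4% |
| Gestational diabetes | >99.0% | 351 | 98.9% |
| Preterm birth | >99.0% | 316 | 99.5% |
| SGA, postnatal growth deficiency | >99.0% | 316 | 99.9% |

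The 316 is an upper figure for the last two rows. Table 4 also removes multiples and infants with MCM, and for growth deficiency those born preterm or SGA. The margin is large, however: at n = 200 the same formula still gives 95.0% for preterm birth and 97.9% at a 10% rate.

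**Step 3: compare the rates with 90% live births.** Only 10% of pregnancies can end in anything other than a live birth. Termination at 18.6% exceeds that by itself. The external comparison in Table 4, "Comparison with external comparator (CDC Abortion Surveillance System"), divides by live births, so 18.6% might be such a ratio. It would then be 0.186 × 0.9 = 16.7% of pregnancies, or 0.186 / 1.186 = 15.7% if only live births and terminations are counted. Both still exceed 10%. SAB at 13.4% could fit alone only if at most 0.10 / 0.134 = 75% of women enrolled before 20 weeks and there were no other losses.

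**Step 4: what the 90% assumption allows.** After stillbirth, SAB and termination share 10% − 0.6% = 9.4%. Solving the formula at n = 351, power above 99% needs a reference rate of about 7.0%, and power above 80% about 3.3%. Two rates of 7.0% make 14.0%, so on the full denominator both cannot have the stated power.

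**Step 5: a range for SAB and termination at n = 351.** The protocol gives no registry rates for either, so these are assumptions.

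- Proportional split of 9.4%: SAB 9.4 × 13.4 / 32.0 = 3.9%, power 87%; termination 9.4 × 18.6 / 32.0 = 5.5%, power 96%.
- The same SAB events, all among an assumed half of women enrolled before 20 weeks (n about 176, rate 7.9%): power 90%.
- Termination at 2%: power 58%. Termination at 1%: power 33%.

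**The case against.** The best defence is that Table 3 contains no calculation error and hides nothing. It names 390 women, labels its rates as general-population rates and stands below a paragraph that explains the attrition. Sample size rests on MCM alone. Section 9.7 calls secondary p-values nominal and asks for 95% confidence intervals, which will show the precision actually achieved. All of this stands, and it limits the point to inconsistent assumptions.

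A reader might infer more than the documents support, in four ways.

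- *That the >80% statement fails after loss.* It does not. At the stated rates and method every listed secondary outcome that was above 80% stays above it. Pre-eclampsia is closest, and its Table 4 denominator is women with a known outcome (351), not live births (316).
- *That pre-eclampsia falls below 80% under Fisher's test.* The figure of 78.5% at 351 changes sample size and method together. Fisher at the full 390 already gives 83.3%, against a table that declares the normal approximation for this row.
- *That Table 3's rates cut the MCM sample to 237 and its power to 68%.* That calculation adds rates with different denominators and overrides the section's cited 90% live-birth figure.
- *That the MCM power of 71.9% for a 2.5-fold risk at 316 is undisclosed.* Table 2 already covers that case by moving to 2.7-fold.

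It can also be said that the >80% sentence is meant to cover only the tabulated outcomes. That is a fair reading, but the wording does not limit it so.

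**Conclusion.** The point holds as one of inconsistent and optimistic assumptions in the secondary-outcome power table. Loss alone takes pre-eclampsia from 85.5% to 81.6% and puts gestational hypertension and diabetes just under the stated 99.0%. These shifts are small and overturn no conclusion. The more substantial defect is in the SAB and termination rows. Their rates cannot hold together with 90% live births, and the claim of over 99% power for both is unsupported on the full denominator. What the power would be is open: both exceed 80% under a proportional split, but either falls below 80% at n = 351 if its reference rate is under about 3.3%.

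The conclusion rests on the protocol's own 10% loss and 90% live births, the pooled normal approximation that reproduces its table, and, for SAB and termination only, the assumed rates shown above. The sizing of the primary outcome is unaffected.

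**What to change.** Restate Table 3 with a column giving each outcome's Table 4 denominator: at most 351 women with a known outcome, about 316 live births, and fewer where the denominator is restricted further. Replace the SAB and termination rates with values per enrolled pregnancy that are compatible with 90% live births, and show power over a range because the registry rates are unknown. Cross-refer the MCM row to the 316 case in Table 2. Limit the >80% sentence to outcomes for which power was calculated and holds, or add rates for minor malformations and developmental delay.

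The cost is one table and one sentence, with somewhat less favourable figures. Enrolment targets and analyses stay as they are.
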